9.6. Enrollment and dropout

All participants will be enrolled in the first 36 months of the study to allow for a complete 28 weeks of observation for each subject. To decrease variability, we will only enroll individuals who have remained suppressed with no viral loads >50 copies/ml 48 weeks before enrollment. Viral loads are performed as part of recently funded 'ART NET' study in San Diego (1R01MH100974-01A1, PI [name]) every 6 months and in the Owen clinic every 3 months, and we will have access to both measures. Anticipating a 10% dropout, we will enroll 56 subjects into our RCT. We thus conservatively expect to achieve an evaluable sample size of 50 at study end.

9.7 Clinical Site

All study visits will take place at the UCSD Antiviral Research Center (AVRC) located at [name].

10. STUDY POPULATION

10.1 Inclusion/Exclusion Criteria

10.1.1 Participant Inclusion Criteria

- 10.1.1.1 Documented HIV-1 infection more than 365 days ago (HIV antibody or viral load positive).
- 10.1.1.2 Capable of signing written informed consent.
- 10.1.1.3 Documented viral suppression for at least 48 weeks (\leq 50 copies/mL)

- 10.1.1.4 Men and women between 18 and 65 years of age.
- 10.1.1.5 Read and comprehend English.
- 10.1.1.6 Documented CD4 count at enrollment (>250 cells/ μ l)
- 10.1.1.7 Reported CD4 nadir >100 cells/ μ l.
- 10.1.1.8 Received seasonal flu vaccination at least 6 weeks prior to first trial injection (and not more recently)
- 10.1.1.9 Received vaccination for pneumococcal disease at least 12 months prior to first trial injection (and not more recently)
- 10.1.1.10 Started ART >6 months from estimated date of infection)

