6. PROTOCOL SUMMARY

Title: Perturbing the HIV Reservoir

Sample Size: 56

Study Population: HIV-infected individuals between 18 and 65 years old who started antiretroviral therapy (ART) during chronic infection (at least one year from estimated date of infection) and remained virally suppressed for at least 48 weeks before enrollment. Participants will have CD4 >250 cells/ μ l at enrollment and a CD4 nadir >100 cells/ μ l.

Participating Sites: UCSD's Antiviral Research Center (AVRC)

Study Design: The proposed study is a randomized double-blinded controlled trial conducted over 28 weeks. Randomized interventions will be injections of Influenza vaccine, Pneumococcal vaccine, and Placebo. Each participant will receive each injection but in a randomized order. See Figure 1 below.

Schedule of Evaluations: Study evaluations will be based on three 30 day cycles (Influenza vaccine, Pneumococcus vaccine, Placebo in random order) over 28 weeks of the RCT. *Pre injection:* one paired blood, optional stool and optional genital secretion sample will be collected before each injection. *Post-injection:* Blood will be collected on days 2, 4 and 7 while paired blood and optional genital secretion samples will be collected on days 14 and 30 after each injection.

Table 1. Perturb Study - Schedule of Evaluations																				
Activity	Screening	Cycle 1 Treatment Period Fluarix/Fluzone, Pneumovax 23 or Placebo ^a						Cycle 2 Treatment Period Fluarix/Fluzone, Pneumovax 23 or Placebo ^c						Cycle 3 Treatment Period Fluarix/Fluzone, Pneumovax 23 or Placebo ^c						Premature Discontinuation
		Baseline (Day 0)	Day 2 ^b	Day 4 ^b	Day 7 ^b	Day 14 ^b	Day 30 ^b	Week 12 (Day 0)	Day 2 ^b	Day 4 ^b	Day 7 ^b	Day 14 ^b	Day 30 ^b	Week 24 (Day 0)	Day 2 ^b	Day 4 ^b	Day 7 ^b	Day 14 ^b	Day 30 ^b	
Informed Consent	X																			
Eligibility Checklist	X																			
Medical Release	X																			
Vaccination History	X																			
Randomization	X																			
Blood collection ^d		X	X	X	X	X	X	X	X	X	X	X	X	X	X	X	X	X	X	X
Pregnancy test ^e	X																			
Physical Exam		X	X	X	X	X	X	X	X	X	X	X	X	X	X	X	X	X	X	X
Medical History, Health Survey	X	X	X	X	X	X	X	X	X	X	X	X	X	X	X	X	X	X	X	X
Concomitant Medications		X	X	X	X	X	X	X	X	X	X	X	X	X	X	X	X	X	X	X
ARV Adherence		X	X	X	X	X	X	X	X	X	X	X	X	X	X	X	X	X	X	X
Post-vax Symptoms		X	X	X	X	X	X		X	X	X	X	X		X	X	X	X	X	X
Adverse Events		X	X	X	X	X	X	X	X	X	X	X	X	X	X	X	X	X	X	X
Study Drug Injection		X						X						X						

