9.4. Study population

This study will enroll 56 HIV-infected individuals between the ages of 18 and 65 who started ART during chronic infection. These subjects will be recruited from both the UCSD AntiViral Research Center and the Owen Clinic. Eligible participants will have CD4 >250 cells/ μ l at enrollment and a CD4 nadir >100 cells/ μ l. We chose to limit enrollment to younger individuals with higher CD4 counts to enhance the likelihood of having a more robust immune response to any given vaccine. We limited enrollment to individuals who started ART during chronic infection (at least one-year from estimated date of infection) to enhance the likelihood of having a large replication competent viral reservoir, thus increasing our chances to observe an effect of vaccine administration on HIV RNA transcription [96]. To reduce variability in vaccine stimulation (between antigen naïve versus experienced participants), we will also limit participation to individuals who have documented or reported vaccine history consistent with previous influenza and pneumococcal vaccination.

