10.2 Recruitment Process

Subjects will be recruited from the UCSD AVRC and the Owen Clinic. Owen Clinic is an HIV care program affiliated with UC San Diego Health System. It offers HIV primary care in addition to a number of services such as ART therapy, mental health services, medication adherence and substance abuse counseling. Subjects visiting either AVRC or the Owen clinic who are known to be HIV positive and meet the inclusion criteria will be recruited to this study and a screening visit will be scheduled.

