12.3.1 Screening

At screening a survey will establish inclusion and exclusion criteria. A screening CRF checklist and a screening survey will be completed by nursing staff. The screening visit will involve a discussion of vaccination history and medical history relevant to the inclusion and exclusion criteria. In addition documentation of plasma HIV-1 RNA and CD4+ T-cell counts will be recorded in the source documents and electronic CRF. A urine pregnancy test will be performed at screening in women who can become pregnant and will be repeated only if pregnancy is suspected.

Written informed consent explained by trained clinical staff will occur before starting screening procedures. The baseline visit (study entry) and administration of the vaccine or vaccine-placebo intervention will be performed within 30 days of the screening visit.

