15. STATISTICAL CONSIDERATIONS

15.1 Overview and General Design Issues

The proposed study is a randomized double-blind controlled trial conducted over 28 weeks. Randomized interventions will be injections of Influenza vaccine, Pneumococcal vaccine, and Placebo. Each participant will receive each injection but in a randomized order.

Vaccines: Influenza (Fluarix®, GSK), Pneumococcal (Pneumovax®23, Merck), and placebo (sterile saline injection).

Primary endpoint: average level of CD4+ T-cell-associated HIV RNA transcription measured at day 7 after each injection.

Study Arms: Each subject will take Influenza (Fluarix®, GSK), Pneumococcal (Pneumovax®23, Merck), and placebo. Randomization will determine the order in which the subjects receive the injections. There are six potential study arms, one for each possible combination in which someone could receive the injections.

Study population: This study will enroll 56 HIV-infected individuals between the ages of 18 and 65 who started ART during chronic infection. These subjects will be recruited from the UCSD AVRC. Eligible participants will have CD4 >250 cells/μl at enrollment and a CD4 nadir >100 cells/μl. We chose to limit enrollment to younger individuals with higher CD4 counts to enhance the likelihood of having a more robust immune response to any given vaccine. We limited enrollment to individuals who started ART during chronic infection (>365 days from estimated date of infection) to enhance the likelihood of having a large replication competent viral reservoir, thus increasing our chances to observe an effect of vaccine administration on HIV RNA transcription [96]. To reduce variability in vaccine stimulation (between antigen naïve versus experienced participants), we will also limit participation to individuals who have documented or reported vaccine history consistent with previous influenza and pneumococcal vaccination.

Sample collection: Study evaluations will be based on three 30 day cycles (Influenza vaccine, Pneumococcus vaccine, Placebo in random order) over 28 weeks of the RCT. *Pre injection:* one paired blood, optional stool and optional genital secretion sample will be collected before each injection. *Post-injection:* Blood samples will be collected on days 2, 4, 7, 14 and 30 after each injection. Optional genital secretion samples will be collected on days 14 and 30 after each injection

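### The inclusion criteria admit people who started ART more than 6 months after infection, while three other sections limit enrolment to one year or later

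*Combined protocol and SAP*

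**What the plan says.** Four places in the combined protocol and SAP put a number on the time from estimated infection to ART start:

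- Section 10.1.1, criterion 10.1.1.10: "Started ART >6 months from estimated date of infection".
- Section 6, Protocol Summary: "during chronic infection (at least one year from estimated date of infection".
- Section 9.4: "We limited enrollment to individuals who started ART during chronic infection (at least one-year from estimated date of infection".
- Section 15.1: "started ART during chronic infection (>365 days from estimated date of infection".

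Sections 9.4 and 15.1 also give the reason for the limit. People who started treatment in chronic infection are more likely to carry a large replication-competent reservoir, which should make a vaccine effect on HIV RNA transcription easier to see. Section 7.1.2 also counts ART start in chronic infection among the features of this study that address weaknesses of earlier work, but gives no threshold there.

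Two other inclusion criteria involve time: 10.1.1.1, "Documented HIV-1 infection more than 365 days ago", and 10.1.1.3, "Documented viral suppression for at least 48 weeks". Under section 10.2, clinic patients who "meet the inclusion criteria will be recruited to this study".

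**The concern.** Two different limits apply to the same interval, measured from the same starting point. The looser one sits in the list that screening staff use, and the stricter one in the text that describes and justifies the population. If section 10 is followed as written, people who started ART between 6 and 12 months after infection can be enrolled, although sections 9.4 and 15.1 say enrolment was restricted to keep them out.

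Two things are at stake. First, a report that takes its population description from the Summary, 9.4 or 15.1 could misstate who was studied. Second, if the plan's own reasoning about reservoir size is right, early starters could respond less and pull the average change in cell-associated HIV RNA towards zero. Section 7.1.2 blames mixed earlier results partly on heterogeneous populations, including differing durations of infection, so the definition of chronic infection is part of the design argument.

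**Working it through.** The plan calculates no figure on this point. The check compares the texts and then asks whether any other criterion closes the gap.

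**The four statements side by side**

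| Place | Minimum time from infection to ART start | Admits a start on day 200? |
|---|---|---|
| 10.1.1.10 | more than 6 months | yes |
| Protocol Summary | one year or more | no |
| 9.4 | one year or more | no |
| 15.1 | more than 365 days | no |

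There is also a one-day difference among the last three: the Summary and 9.4 admit a start at exactly one year, and 15.1 does not.

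**Could another criterion enforce one year?** Criterion 10.1.1.1 contains the figure 365 days, but it limits how long ago infection was documented. Section 12.3.3 confirms that it counts back from enrolment. It says nothing about the gap between infection and ART start. The exclusion list in 10.1.2 does not mention when ART was started.

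**Date arithmetic**

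Inputs: 6 months = 365.25 / 2 = 182.6, taken as 183 days (10.1.1.10); one year = 365 days (Summary, 9.4, 15.1); 48 weeks = 48 × 7 = 336 days (10.1.1.3).

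- Disputed window: 365 − 183 = 182 days.
- Earliest enrolment after infection = ART-start threshold + suppression period. Under 10.1.1.10: 183 + 336 = 519 days. Under the one-year wording: 365 + 336 = 701 days. Both are lower bounds, because they treat suppression as starting on the day ART starts.
- Criterion 10.1.1.1 is met when (days from documented diagnosis to suppression) + 336 > 365, that is, when that gap is 30 days or more.

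**A worked case.** The diagnosis and ART-start days are chosen for illustration. Infection is on day 0, diagnosis is documented on day 150 and ART starts on day 200.

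- Earliest enrolment: 200 + 336 = day 536.
- Time since documented infection: 536 − 150 = 386 days, more than 365, so 10.1.1.1 is met.
- Suppression: 336 days, so 10.1.1.3 is met.
- ART start: 200 days, more than 183, so 10.1.1.10 is met.
- One-year limit: 200 is less than 365, so the limit in the Summary, 9.4 and 15.1 is failed.

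If suppression takes a further 60 or 180 days, documented infection is 446 or 566 days old at enrolment. Delay only makes 10.1.1.1 easier to satisfy.

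**Effect on the primary analysis.** Section 15.8.2 uses paired t-tests, and each participant is to receive both vaccines and placebo, so the timing of ART does not bias the within-person contrast. The sample-size inputs in section 15.4 (50 evaluable participants, pooled SD 625) do not use the ART-start threshold. The documents give neither the share of candidates in the 182-day window nor how such people respond, so no dilution or loss of power can be computed.

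**The case against.** The strongest reply is that no harm is shown: the comparison is unbiased, the sample size does not depend on the threshold, and dilution is only conditional. That is correct, and the finding claims no more.

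A second reply is that three places against one does not show which limit is intended. The population paragraphs in 9.4 and 15.1 are almost the same text, so they are hardly independent, and the 6-month criterion may be a deliberate relaxation. This also stands, and it is why the choice belongs to the sponsor. It does not remove the conflict: if 6 months is intended, the Summary, 9.4 and 15.1 are wrong and need correcting.

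A third reply concerns the remedy. If 6 months is kept, early starters are part of the intended population. Repeating the tests without them would not directly test whether they respond differently; that would need a comparison between subgroups of unknown size. This has some force. The analysis shows only whether the result holds in the population for which the rationale was written. Its case is strongest where one year is adopted after people have entered under 6 months.

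Finally, the two dates may already be collected, since 10.1.1.10 cannot be checked without them and the screening forms are not shown. That is possible.

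**Conclusion.** The concern holds. The eligibility rule in section 10 and the population stated in the Summary, 9.4 and 15.1 differ over a window of about 182 days of ART start, and no other criterion closes it. This is more than a slip of wording: applied as written, the rule can enrol people whom the plan says it excluded in order to improve its chance of seeing the primary effect.

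The established consequence is a possible mismatch between the people enrolled and the population described. Dilution of the effect depends on the plan's own premise that early starters carry smaller reservoirs and respond less, and it cannot be sized from the documents. The day counts take 6 months as 183 days and suppression from the first day of ART. The correction should be made, but it does not threaten the validity of the paired comparison.

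**What to change.** 1. The sponsor chooses one threshold and states it in the same words in the Protocol Summary, 9.4, 10.1.1.10 and 15.1, including whether exactly one year qualifies if a one-year limit is adopted. If 6 months is kept, the population statements in those three other sections change, and so does the rationale in 9.4 and 15.1, which is now tied to one year.
2. Record the estimated date of infection and the ART start date at screening. Section 12.3.1 says that "documentation of plasma HIV-1 RNA and CD4+ T-cell counts will be recorded in the source documents and electronic CRF" and mentions vaccination and relevant medical history, but does not name these two dates. If the forms already capture them, nothing is added.
3. If 6 months is kept, or if anyone was already enrolled under the 6-month wording, repeat the two primary paired comparisons without participants who started ART before 365 days, as a sensitivity analysis. If one year is adopted and nobody entered under the 6-month wording, this is not needed.

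The cost is small: one amended criterion, or three corrected statements if 6 months is kept, plus two dates at screening and at most one repeat of a simple analysis. Adopting one year might slightly reduce the number of eligible candidates.

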10.1.2 Participant Exclusion Criteria

- 10.1.2.1 Uncontrolled psychiatric condition.
- 10.1.2.2 Under the influence of drug(s) or alcohol at time of screening.
- 10.1.2.3 Any condition that, in the opinion of the investigator, would limit follow-up and adequate consent.
- 10.1.2.4 History of allergic reactions to any of the proposed vaccines or egg allergy.
- 10.1.2.5 History of Gullian Barre syndrome.
- 10.1.2.6 Receiving immunosuppressive medications.
- 10.1.2.7 Pregnancy or lactation.

10.1.3 Co-enrollment Criteria

Co-enrollment in this study and other studies (other than ART NET as discussed above) will be discussed with the protocol team and will be decided on a case-by-case basis.

10.2 Recruitment Process

Subjects will be recruited from the UCSD AVRC and the Owen Clinic. Owen Clinic is an HIV care program affiliated with UC San Diego Health System. It offers HIV primary care in addition to a number of services such as ART therapy, mental health services, medication adherence and substance abuse counseling. Subjects visiting either AVRC or the Owen clinic who are known to be HIV positive and meet the inclusion criteria will be recruited to this study and a screening visit will be scheduled.

10.3 Participant Retention

If a subject meets the inclusion criteria and completes all activities of the screening visit, the study clinician will personally assist the patient in scheduling follow-up visits in order to increase participant retention. The subject will be compensated for each follow up visit according to the following table. Each participant has the opportunity to complete this 30 day cycle a total of three times, one for each study vaccine and placebo. The total amount each participant may be compensated is \$570 (\$190 for each cycle); see **Table 2** Participant Compensation.

Study Visit	Laboratory Procedure	Compensation
Baseline	Blood Draw, optional Genital Secretion, optional stool, Intramuscular Injection	\$50
Day 2	Blood Draw	\$20
Day 4	Blood Draw	\$20
Day 7	Blood Draw	\$20
Day 14	Blood Draw, Optional Genital Secretion	\$30
Day 30	Blood Draw, Optional Genital Secretion	\$50

11. INTERVENTIONS

11.1 Biomedical Interventions

11.1.1 Regimen

Each study subject will receive one dose each of the following: Pneumovax®23, Fluarix® (or Fluzone®), and placebo (sterile saline solution). These will be administered at the baseline visit (Day 0) of each cycle and will precede 30 days of follow-up. After the 30 days of each cycle, there is a washout period (minimum 6 weeks) before the next cycle begins. Each study drug will be administered as a one time intramuscular injection.

NOTE: Fluarix® quadravalent vaccine is the flu vaccine of choice for this study. Fluzone® quadravalent vaccine may be substituted for Fluarix® only in the event that Fluarix® is unobtainable from the wholesaler/manufacturer.

11.1.2 Study Product Formulation and Preparation

In order to achieve double blind administration of the vaccines, each drug or placebo will first be transferred to generic, non-labeled syringes by the Study Pharmacist before being delivered to the clinical staff who will administer the injection. This preparation (along with preparation of the sterile saline placebo) will take place in the AVRC pharmacy. No after-market modifications will be made to the formulation of Pneumovax®23 (Merck) or Fluarix® (GSK), or Fluzone® (Sanofi Pasteur) vaccines.

11.1.3 Device Studies: (Not applicable)

11.1.4 Study Product Supply and Accountability

All study product supply will be stored and handled by AVRC pharmacy staff. All pharmacy procedures will be done in accordance with existing verified Standard Operating Procedures (SOPs) that pertain to pharmacy inventory, storage, security and accountability.

11.1.5 Assessment of Participant Adherence with Study Intervention

Since the study intervention (intramuscular injection) will only be administered three times and always with a study clinician present, there is no need to assess participant adherence aside from attending the baseline visit of each study regimen cycle.

11.1.6 Concomitant Medications and Procedure

All concomitant medications will be recorded (including start/stop date, medication type, dose and indications) in a Concomitant Medications Flowsheet (see Appendix A. CRF #CON030). Whenever a concomitant medication or study product is initiated or the dose changed, investigators must review the concomitant medications' and study products' most recent package inserts, investigator's brochure, as well as updated information from DAIDS to obtain the most current information on drug interactions, contraindications, and precautions.

11.1.7 Permitted Medications and Procedures

Because it may interfere with the findings of the study, participants are asked to refrain from receiving routine vaccinations during the study unless otherwise instructed by their primary physician. However, vaccination outside the study protocol will not result in discontinuation of the study. Instead, these instances will be identified and documented, and investigators will control for this instances during analysis. Similarly, any change in any medication, including gain or loss, will be recorded on the Medical History CRF (See Appendix B).

11.1.8 Prohibited Medications and Procedures

Medications that have been suggested to perturb the HIV reservoir or the immune system will require early discontinuation of the study. These medications include: disulfiram, histone deacetylase inhibitors, other cancer chemotherapies, biologic immunosuppressives, high dose steroids etc. Other medications or therapies that are taken will be documented during the study, and will be reported to the PI.

11.1.9 Precautionary Medications and Procedures

Other medications that have been suggested to perturb the HIV reservoir or the immune system, like antibiotics, non-steroidal anti-inflammatory drugs, aspirin, or low dose steroids, will be noted and accounted for in the final analyses.

11.1.10 Required Medications

Study participants must be on ART. Moreover, their HIV therapy must remain successful throughout the study (CD4 count >250 cells/ml and nadir >100 cells/ml). The study participants must also have a recent vaccination history including previous seasonal flu vaccination and previous pneumovax vaccination at least 12 months prior to screening visit.

